### **5.2 Statistical Methods:**

All statistical analysis will be done in an intention-to-treat fashion. No interim analyses are planned. For all statistical tests, a P value of .05 will be considered significant. A Student t-test will provide an unadjusted estimate of the difference between treatment arms. Analysis of covariance, a more robust method that allows control for key differences in baseline characteristics, will be used to provide adjusted comparisons.

Like the primary outcome, continuous secondary outcomes (such as safety and efficacy) will be modeled by t-tests and analysis of co-variance.

Any relationship of the anastomotic leakage with other possible adverse factors will be evaluated by univariate and multivariate regression analysis

When the complete case analysis will exclude more than 5% of patients due to missing data, exploratory analyses to investigate the effect of missing data will be performed. In order to explore the mechanism of the missing data and the validity of a complete case analysis for each end point, patient characteristics will be compared between those with and without missing data and multilevel logistic regression models will be used to identify any associations between prognostic variables and to inform if data are missing at random.

Multilevel logistic regression will be used to estimate the odds ratios (ORs) for conversion to laparotomy, intraoperative complications, and postoperative complications between treatment groups.

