### **1. Background**

Colorectal cancer (CRC) is the second most common cause of cancer-related death in male and the third in females in Western Countries accounting for more than 500,000 deaths in 2013 worldwide(1).

One of the most worrying postoperative complication in colorectal surgery is the anastomotic leak which can occur in about 10-15% of the cases(2).

This complication severely impact clinical outcomes with increased risk of death or permanent stoma, higher risk of local recurrence) and relevant increase in hospital costs (length of hospital stay, admission to intensive care, re-interventions)(3).

The problem of anastomotic leak is particularly relevant in rectal surgery. The more distal the anastomosis, the higher the likelihood of failure, with resection of a distal rectal cancer having almost a five-fold increased risk of anastomotic leak compared with resection for colon cancer(4).

In fact, anastomotic Leakage (AL) is the most severe complication after Low anterior resection of rectum for cancer, occurring between 3 and 24 % of patients(5).

Many risk factors have been recognized in the onset of this complication(6), including gender (male patient have a higher anastomotic leak rate)(7), malnutrition, obesity an diabet, ASA score, tobacco use, cardiovascular disease, immunosoppression, use of NSAID(8), preoperative pelvis radiation.

Other intraoperative risk factors considered are the splenic flexure mobilization with proximal ligation of the IMA(9), positive intraoperative Air-Leak Test(10) and the perfusion of the anastomosis (11).

Temporary fecal diversion has also been suggested (although a diverting stoma mitigates the clinical consequences of an anastomotic leak but does not prevent it(12).

Other intraoperative technical factors include the use of single or double stapled anastomotic techniques, with or without transanal reinforcing sutures(13).

Therefore, preventing the anastomotic leak can bring benefits to the patient and the health system.

All the risk factors described above rapresent the rationale that justifies the use of intraoperative procedures to prevent the anastomotic leak, such as additional manual stiches to the mechanical suture and / or patches of collagen (proper reinforcement or buttressing) or of sealants.

Several attempts have been proposed to reduce the risk of AL in low rectal cancer surgery including

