## **6 STATISTICAL ANALYSIS**

### **6.1 Sample Size Determination:**

The mean percentage of anastomotic leak after rectal cancer is 16% and its reduction to 10% is considered to be clinically significant. Therefore, the interval of confidence calculated is 12. A sample size calculation shows that 67 subjects per arm will suffice for accepting of the hypothesis with a power of 0.8 and a type I error probability of 0.05, with a Confidence level of 95% (sample size calculated by R Studio Version 1.1.419 – © 2009-2018 RStudio, Inc.). Accounting for a predicted 5% estimated loss to follow-up, a total of 138 (134+4) patients will be included in the study.

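### The search for leak risk factors is open-ended, tests every factor at .05 and rests on about 17 expected leaks: a cheap, low-priority wording fix.

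*Combined protocol and SAP*

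**What the plan says.** Section 5.2 (Statistical Methods) plans the risk-factor analysis in one sentence: "Any relationship of the anastomotic leakage with other possible adverse factors will be evaluated by univariate and multivariate regression analysis". The rule for judging it is general: "For all statistical tests, a P value of .05 will be considered significant". The section gives no candidate list, selection rule, limit on model size, penalisation or multiplicity rule for this analysis. It uses the word exploratory for the missing-data work, but not here. It also names multilevel logistic regression for conversion and complications, but does not name the type of regression for leak risk factors.

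The only list of leak risk factors is in section 1 (Background), introduced by "Many risk factors have been recognized in the onset of this complication". Section 5.2 does not refer to it.

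Section 6.1 (Sample Size Determination) fixes the number of events. It assumes 16% leaks without glue, states that "its reduction to 10% is considered to be clinically significant", and concludes that "67 subjects per arm will suffice for accepting of the hypothesis".

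**The concern.** Leak is a yes/no outcome with few events. A regression that may take in any number of factors, each tested at .05, invites two different errors. One is the chance finding: a factor unrelated to leak is declared significant because many were tried. The other is instability: with about one event per coefficient, ordinary logistic regression can fail to converge, or return very large odds ratios with very wide intervals. In either case a chance association could be published as an independent risk factor for leak, and surgeons could use it to judge which patients are at risk.

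**Working it through.** **The plan's own figure.** For 16% v 10% with 80% power and two-sided alpha 0.05, the usual two-proportion formula gives 492 per arm (388 one-sided), not 67. The 67 matches a one-sample precision formula: 1.96² × 0.25 / 0.12² = 66.7. That is a separate and more serious matter. Here 67 per arm is taken as given, because it sets the number of leaks.

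**Expected leaks.**
- Planned rates: 67 × (0.16 + 0.10) = 17.4. The 95% sampling range is 10 to 25.
- After 5% loss from 138: 65.5 × 0.26 = 17.0.
- Both arms at 16%: 67 × 0.32 = 21.4. Both at 10%: 67 × 0.20 = 13.4.

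**Candidate factors in the Background.**
- Ten patient factors: sex, malnutrition, obesity, diabetes, ASA score, smoking, cardiovascular disease, immunosuppression, NSAIDs, pelvic radiation.
- Five or six operative factors: splenic flexure mobilisation and IMA ligation (one item or two), air-leak test, perfusion, stapling technique, transanal reinforcing sutures.
- Total 15 or 16, or up to 18 with anastomotic height and diversion.

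**Events per factor.** 17.4 / 16 = 1.1. Over 10 to 18 factors and 13.4 to 21.4 leaks, the range is 13.4 / 18 = 0.7 to 21.4 / 10 = 2.1. The picture does not depend on the exact count.

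**Problem 1, multiple testing.** The chance of at least one false factor among k independent null tests at .05 is 1 − 0.95^k:
- k = 10: 40%
- k = 15: 54%
- k = 16: 56%

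Sample size does not enter this formula. As a check, a simulated 16-factor analysis with 984 patients (984 × 0.13 = 128 leaks, 8 per factor) still gave a false factor in 58% of trials.

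**Problem 2, few events per factor.** Simulated trials had 134 patients at the planned rates, with arm plus independent binary factors, fitted by maximum likelihood (ML) or by Firth. The documents give no factor prevalences, so two assumed ranges were used: 20–50% and 10–60%. Divergence means non-convergence or an extreme coefficient or standard error; the cut-off differed between runs. In the first three rows every factor is null (prevalence 20–50%, 3,000 trials each, false factors counted among fits that converged). In the others one factor has a true OR of 2 and the rest are null.

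| Model | ML fits diverging | At least one false factor | 5–95% range of estimated OR (true OR 2) |
|---|---|---|---|
| Arm + 2, all null | 3% | 6% | – |
| Arm + 10, all null | 7% | 35% | – |
| Arm + 16, all null | 9% | 57% | – |
| Arm + 2, one true | under 1% to 2% | 3–5% | ML 0.8–6.2 |
| Arm + 11, one true | 5–29% | 33–40% | ML 0.65–7.2 to 0.8–8.9; Firth 0.8–5.1 to 0.8–5.4 |
| Arm + 16, one true | 6–30% | 56–59% | ML 0.7–9.8; Firth 0.8–5.3 |

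The lower divergence figures go with prevalence 20–50% and the higher ones with 10–60%. In the all-null 16-factor model the error per coefficient was about 6%, close to nominal. The largest spurious odds ratio was typically about 4.9 (or its inverse), against about 1.9 with two null factors.

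**The case against.** The strongest objection is about cause. A reader might infer that 17 leaks is what produces the false risk factors. The figures do not support this: ten null tests give 40% with unlimited data, and the 33–40% simulated with ten null factors is no higher. Comparing that with 3–5% in the two-factor model is also unequal, because only one null factor is tested there. This objection stands, and it is why the two problems must be kept apart.

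A reader might also infer that the plan will fit all 16 factors together. It does not say so. Section 5.2 never cites the Background, and the protocol limits some of the items: section 4.2.1 specifies a Knight-Griffen anastomosis, section 4.2.1.1 rules out reinforcement in controls, and no perfusion measurement is described. Sixteen is an upper reading. Univariate and multivariate may also mean screening first. In simulation, screening at .05 almost removed divergence, but 28–38% of trials still kept a false factor and odds ratios were inflated. The fault changes form under that reading but does not go away.

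Three further points stand. Divergence depends on assumed prevalences, so only a range can be given. Cutting to two factors gains little precision by itself: the ordinary fit still spans 0.8–6.2, and the upper/lower ratio of a 95% interval is typically about 11, against about 14 with 16 factors. And the root cause of the few events is the sample size: 492 per arm would give 492 × 0.26 = 128 leaks and relieve most of the instability, though not the multiple testing.

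**Conclusion.** The point holds as a low-priority improvement. With an open set of factors, every test at .05 and about 17 expected leaks, the planned analysis cannot give reliable risk factors, whether read as one full model or as screening followed by a model. The chance of a false factor is about 40% with ten null factors and 54–59% with fifteen; this assumes independent factors and does not depend on sample size. Instability is the separate effect of few events: 5–30% of 11- to 16-factor fits diverge, depending on assumed prevalence, and the 95th percentile of the estimate of a true OR of 2 is about 7–10 by ordinary fitting, against about 5 with Firth. These figures assume logistic regression, which the plan does not name here but which suits a yes/no outcome.

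The documents do not support two stronger conclusions that a reader might draw. The randomised comparison is not biased, because this is a secondary analysis. Nor can it be said that the trial will present spurious factors as its conclusions: sections 3.2.1 and 3.2.2 do not list risk-factor identification as an endpoint, and the .05 sentence is a general rule.

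**What to change.** Replace the sentence in section 5.2 with wording to this effect: leak will be analysed in one logistic model containing treatment arm and two factors named here (for example sex and preoperative pelvic radiation, both given in the Background), fitted by Firth penalised likelihood; other factors will be tabulated by leak status with confidence intervals, without P values and without univariate selection; this analysis is hypothesis-generating. Name the factors before any outcome data are seen, so that the choice cannot follow the results.

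Two is not a magic number, and another small pre-named set would be defensible. What matters is the fixed list, the cap, the penalised fit and the label. By the common guide of 10 events per variable (an assumption, not in the documents), 17.4 leaks support one or two factors; at 5 per variable, about three.

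The cost is SAP wording only: no added patients, visits or data. The downside is that fewer factors can be claimed as independent predictors, and intervals stay wide even with two.

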### **5.3 Subject Population for Analysis**

Data analysis will be performed in accordance with the intention to treat principle. If a violation of randomization occurs, all patients will be analyzed according to the original allocation.

The following information will be prospectively collected and reported:

- All-randomized population: Any subject randomized into the study, regardless of whether they receive the intervention.
- Protocol-compliant population: Any subject who was randomized and received both the study intervention and received the required protocol processing.

## **6. ETHICS**

### **6.1 Risks of Participation**

Patients in both study arms will be informed of standard risks of anterior resection surgery, such as ileus, surgical site infections, thrombotic complications, cardiac, or pulmonary complications. In addition, the risk of anastomotic dehiscence will be discussed and the two randomized options to prevent them (suture reinforcement or not) will be carefully described

### **6.2 Institutional Review Boards**

This study will be conducted in accordance to the principles of the Declaration of Helsinki and good clinical practice guidelines. The study protocol will be approved by the Ethics committee of all participating institutions. Prior to randomization, written informed consent will be obtained from all patients.

### **6.3 Data Safety Monitoring Committee**

A data safety monitoring board (DSMB) will be established with experts independent of the authors. The chairman of the DSMB will receive the clinical data forms continuously from the coordinating center and will review data. The DSMB chair may at any time suggest to the Study Chair to terminate the study in case of ethical concerns such as unacceptable complication rates and others.

## **7. AUTHORSHIP AND PUBLICATION**

The rules described herein apply to any presentation of this study. Members of the Protocol Writing Committee as well as Study Chairs qualify for authorship of this study. Vancouver Authorship Guidelines rules shall apply (for full document please see full article at <http://www.icmje.org/index.html>). Surgeons that include patients will attain authorship through a group authorship where names of surgeons will be mentioned. The order of the authors in the group authorship according their active contribution to the trial. The study results may only be published and/or presented as final analyses after the completion of the study, and needs authorization by the study chairs. Publication and/or presentation are defined as any

article, podium presentation, poster, abstract, or any other public presentation of this research. As is generally accepted, members of the DSMB should be independent and not involved in the study in any way including authorship.

